#### 3.3 Exploratory Endpoints/Events/Outcomes

- To evaluate the effects of PHN/TPM on total and visceral body fat
- To evaluate the effects of PHN/TPM vs. placebo + standard treatment on cardiometabolic measures (lipid panel [TC, LDL-C, TG, HDL-C], blood pressure and heart rate).

### 4.0 Study Intervention(s)/Investigational Agent(s)

#### 4.1 Description:

##### *Phentermine/topiramate Therapy*

Participants randomized to PHN/TPM will initiate treatment at 3.75 mg/23 mg orally once daily in the morning for 14 days, which will then be increased to 7.5 mg/46 mg orally once daily in the morning for 14 days, which will then be increased to 11.25 mg/69 mg orally once daily in the morning for 14 days, which will then be increased to 15 mg/92 mg orally once daily in the morning for the remainder of the trial. There will not be a pause in dose titration between weeks 4 and 12 as indicated by the medication labeling as this pause is indicated to clinically assess weight loss response on mid-dose PHN/TPM before up-titrating to high-dose PHN/TPM. However, the goal of this proposed study is to assess BMI reduction on the maximum tolerated dose of PHN/TPM in a clinical research setting. Therefore, an assessment of weight loss on the moderate dose of

PHN/TPM between weeks 4 and 12 is not warranted. Participants unable to tolerate the dosing regimen will be maintained at the maximally tolerated dose. Following the final study visit, all participants will be down-titrated gradually by taking medication every other day for seven days before stopping treatment altogether. PHN/TPM will be purchased from an independent vendor by the University of Minnesota Investigational Drug Service Pharmacy (IDS). Placebo will be manufactured by IDS. The placebo capsules manufactured by IDS will not be able to be matched to the commercial product. The PI and research coordinator will not be involved in pill counting to evaluate adherence for this trial in order to preserve the blinding of investigators. Participants will not be told which treatment arm they are in to preserve the blinding of participants. Participants will be instructed to take the medication under the supervision of a parent/guardian and pill counts of returned product will serve as a proxy of treatment adherence. If the average fasting plasma glucose (FPG), measured by CGM, is >185 mg/dL after titration to PHN/TPM 15mg/92mg or maximum tolerated dose, metformin therapy or basal insulin therapy will be started or titrated for a goal average FPG <110 mg/dL.

#### *Metformin Therapy*

Participants who are on metformin therapy prior to enrollment will remain on metformin, if tolerated. Titration and maximum tolerated dose will be at the discretion of the principal investigator and a dose of 2000 mg daily will be targeted if CGM is > 185 mg/dL after titration to PHN/TPM 15mg/92mg or maximum tolerated dose.

#### *Insulin Therapy*

Insulin will be started per the American Diabetes Association guidelines on any participants whose A1c is >8.5%. For those treated with insulin prior to enrollment, basal insulin dose will be reduced by 20% at start of PHN/TPM therapy and then by 20% every 4 weeks if average FPG is <110 mg/dL. Basal insulin dose will continue to be reduced every four weeks until basal insulin dose is below 0.2 units/kg/day and then basal insulin will be stopped. If the FPG value is >185 mg/dL after titration to maximum tolerated dose of PHN/TPM and metformin, basal insulin therapy will be started or titrated up by 20% until for a goal average FPG <110 mg/dL. If participants are on rapid-acting insulin meal dosing (carbohydrate coverage), this will be discontinued at the start of the PHN/TPM therapy and only restarted if two-hour post-prandial plasma glucose >200 mg/dL. Rapid-acting insulin will be used as a rescue medication for BG >200 mg/dL per PI discretion.

4.2 Drug/Device Handling:

The PHN/TPM that will be used for this study will be stored with the IDS pharmacy. Placebo will be manufactured by IDS. The IDS pharmacy specializes in storing and dispensing investigational drugs for clinical trials. Study physicians will write a prescription in order for IDS to dispense the study medication. IDS is a secure facility (behind two locked doors) and maintains refrigerators and freezers with temperature tracking to assure that the drugs utilized in this study will maintain stability. IDS will keep detailed records on the receipt of investigational product (including lot numbers) and detailed records on the dispensing of product to each subject enrolled in the study. IDS is also equipped to destroy any medication that remains at the end of the study or any product that is returned by the study participants. IDS will also hold the randomization key for the study, which was developed by the study biostatistician, and will follow their internal standard operating procedures for breaking the blind in the event of an emergency.

When an individual participant transitions from the placebo-controlled portion of the study to the open-label portion of the study, the study physician will put in orders for the open label study for IDS to dispense medication and the IDS staff will review the patient randomization and will either continue to fill the prescription with the maintenance dose or fill the prescription to have the participant titrate up on the study medication in order to help keep the study team blinded.

4.3 Biosafety:  
Not applicable.

4.4 Stem Cells:  
Not applicable.

4.5 Fetal Tissue:  
Not applicable

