## 1.0 Objectives

### 1.1 Purpose:

We will conduct a pilot, pragmatic, randomized trial with a 6-month placebo-controlled period followed by a 6-month open-label extension, investigating the effects of phentermine/topiramate (PHN/TPM) on BMI, insulin sensitivity, and glycemic control compared to placebo plus standard treatment (metformin +insulin) in adolescents with T2D. The purpose of this study is to 1) evaluate the effects of PHN/TPM vs. placebo+ standard treatment on BMI in adolescents with T2D and obesity and 2) evaluate the effects of PHN/TPM vs. placebo + standard treatment on insulin sensitivity and B-cell function in adolescents with T2D and obesity.

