### 3.0 Study Endpoints/Events/Outcomes

#### 3.1 Primary Endpoint/Event/Outcome:

- To evaluate the effects of PHN/TPM vs. placebo + standard treatment (metformin ± insulin ± liraglutide 1.8 mg or exenatide ER) on BMI in adolescents with T2D and obesity.

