7.2 Sharing of genetic testing: Not applicable

**8.0 Study Population**

8.1 Inclusion Criteria:

- Ages 12 to  $\leq$  20 years at study entry
- Obesity (BMI  $\geq$  the 95th percentile for age and sex)
- HgbA1c  $\geq$  6.5% at type 2 diabetes diagnosis
- Negative diabetes auto-antibodies
- English-speaking
- For participants of child-bearing potential: when sexually active, agreement to use two forms highly effective contraception (oral contraceptive pill, IUD, implant, and/or condoms) during study participation

8.2 Exclusion Criteria:

- Pregnancy or lactation
- Newly-initiated or change in dose of weight altering medication within past 6 months, including SGLT-2 inhibitors, DPP-IV inhibitors, liraglutide 1.8 mg and exenatide ER
- Current or recent (< six months prior to enrollment) use of anti-obesity medication(s) defined as orlistat, phentermine, topiramate, combination

PHN/TPM, semaglutide, and/or combination naltrexone/bupropion (monotherapy use of naltrexone or bupropion is not an exclusion)

- Current use of sulfonylureas
- Previous metabolic/bariatric surgery
- Current use of a stimulant medication
- History of glaucoma
- Current or recent (<14 days) use of monoamine oxidase inhibitor or carbonic anhydrase inhibitors
- Known hypersensitivity to sympathomimetic amines
- Any history of treatment with growth hormone
- Any history of bulimia nervosa
- Major psychiatric disorder as determined by the local medical monitor
- Unstable and clinically-diagnosed (defined as documented in the medical record, if available) depression or PHQ-9 score  $\geq 15$
- Any history of active suicide attempt, a “yes” answer to Question 4 (Active Suicidal Ideation with Some Intent to Act, Without Specific Plan) on the “Suicidal Ideation” portion of the C-SSR, or a “yes” to answer to Question 5 (Active Suicidal Ideation with Specific Plan and Intent) on the “Suicidal Ideation” portion of the C-SSRS
- History of suicidal ideation or self-harm within the previous 30 days or a “yes” answer to any of the suicide-related behaviors (actual attempt, interrupted attempt, aborted attempt, preparatory act, or behavior) on the “Suicidal Behavior” portion of the C-SSRS and the ideation or behavior occurred within the past month.
- Current pregnancy or plans to become pregnant during study participation
- Current tobacco use
- ALT or AST  $\geq 3$  times the upper limit of normal
- Moderate (Child-Pugh score 7-9) or severe (Child-Pugh score 10-15)

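### The week-0 insulin reduction has no glucose or A1c condition, so on the workable both-arms reading it also applies to insulin-treated placebo participants and to those with A1c above 8.5%

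*Combined protocol and SAP*

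**What the plan says.** The rules are in Section 4.1 of the protocol, under Insulin Therapy. The paragraph opens with a start rule: "Insulin will be started per the American Diabetes Association guidelines on any participants whose A1c is >8.5"%. For those already on insulin, "basal insulin dose will be reduced by 20% at start of PHN/TPM therapy". Further 20% cuts follow at 4-week intervals if average fasting glucose (FPG) is below 110 mg/dL, and basal is stopped once it is under 0.2 units/kg/day. Of mealtime insulin the plan says "this will be discontinued at the start of the PHN/TPM therapy", with a restart if the 2-hour glucose after a meal exceeds 200 mg/dL. The threshold for raising basal begins "If the FPG value is >185 mg/dL after titration to maximum tolerated dose of PHN/TPM and metformin". Finally, "Rapid-acting insulin will be used as a rescue medication for BG >200 mg/dL per PI discretion".

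Other sections also allow insulin to be adjusted. The schedule in 5.1 lists CGM-guided insulin titration at every visit from week 4, 5.2 (Glycemic Control) says CGM data guide insulin and metformin dosing, and 8.3 provides for telephone contact on dose changes at weeks 4 and 8 among others.

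Eligibility (8.1) asks for an A1c of at least "6.5% at type 2 diabetes diagnosis". Neither 8.1 nor 8.2 sets an A1c limit at entry. The comparator is described in 1.1 as "compared to placebo plus standard treatment (metformin +insulin) in adolescents with T2D" and in 3.1 as "placebo + standard treatment (metformin ± insulin ± liraglutide 1.8 mg or exenatide ER) on BMI".

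**The concern.** Reducing insulin when an effective weight-loss drug is started is a sensible precaution against hypoglycaemia. The same reduction on placebo has nothing to offset it, and the plan applies the first step without looking at current control. The participants most exposed are those whose A1c is already above 8.5%. The protocol treats that level as a reason to start insulin in someone not taking it, yet someone at the same level who is taking it has it reduced.

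What is at stake is glycaemic safety in adolescents, in a plan whose background section (2.1) stresses the importance of tight control. The insulin risk text in 12.1 covers hypoglycaemia but not hyperglycaemia caused by the reduction.

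**Working it through.** The plan gives no figure on this point. Its one design figure is power for BMI change (14.2). With SD 8.9 and correlation 0.75, the adjusted SD is 8.9 × √(1 − 0.75²) = 5.887. Fifteen per arm then give power of 0.797 for a 6% difference at two-sided 0.05 (two-sided assumed), which matches the stated 80%. Nothing below changes it.

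**1. Which steps carry a condition.**
- Week-0 basal cut: none. The FPG condition follows the 4-weekly cuts, not the first one.
- Week-0 mealtime stop: none; only the restart has a threshold.
- Later basal cuts: FPG below 110.
- Basal increase with a threshold: FPG above 185, after titration to maximum tolerated dose.
- Rapid-acting rescue: glucose above 200, at the investigator's discretion, from the start.

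Reading the FPG condition back onto the first cut would not help much. Participants are taught CGM at baseline (8.3) and the first scheduled CGM review is week 4, so no trial CGM record need exist at week 0. A1c is drawn at baseline (schedule in 5.1) and is not among the screening bloods (8.3).

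**2. Which arm.** The text names PHN/TPM only. But 4.1 sets out to keep participants and investigators blind, and 4.2 leaves the randomization key with the pharmacy. An investigator without the key cannot cut insulin in one arm. Section 11.1 likewise links insulin adjustment to stopping either PHN/TPM or placebo. Both arms is therefore the workable reading for weeks 0–24, though it is an inference.

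**3. Two people with A1c above 8.5% at baseline.** One not on insulin is started on it. One on insulin has basal cut by 20% and mealtime insulin stopped. No entry criterion on A1c removes the second person.

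**4. Timing.** There are three 14-day steps before the top dose: 3 × 14 = 42 days, or 6 weeks, if every step is tolerated. It is sooner for someone held at a lower dose. Scheduled CGM reviews are at weeks 4, 8, 12 and so on. Week 4 falls before the FPG-above-185 rule opens; week 8 is the first review after it. At week 4 insulin may be titrated on CGM, but no threshold or step for a basal increase is given.

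**5. Size for one participant.** Entry doses are not in the documents, so the values here are assumed.
- Basal after the cut is 0.80 × entry dose. The stop limit is reached when 0.80 × entry < 0.2, that is, entry < 0.2/0.80 = 0.25 units/kg/day. Entry at 0.20 gives 0.16 and at 0.24 gives 0.192, both below the limit, so the written rule would stop basal at once. Entry at 0.25 gives 0.20, which is not below it.
- With basal share b of total dose, the day-one fall is 0.2b + (1 − b). For b = 1, 0.75 and 0.5 this is 20%, 40% and 60%.
- One 20% upward step from the cut dose gives 0.80 × 1.20 = 0.96 of the entry dose.

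**The case against.** The strongest reply is that the plan does not leave these participants unattended. CGM-guided insulin titration runs from week 4 with no limit on direction. Mealtime insulin can restart, and rapid-acting rescue is open from day one. Metformin titration is at the investigator's discretion. The first cut has a rationale, since 12.1 notes that weight loss raises hypoglycaemia risk in insulin users. The start rule and the reduction rule address different people, so there is no direct contradiction. The investigator may also exclude anyone judged at risk (8.2).

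Most of this stands. A reader might infer that basal cannot be raised until titration ends, or that it stays at 80% of the entry dose for a third or all of the placebo-controlled period. The documents do not support that: 5.1, 5.2 and 8.3 allow adjustment from week 4. What is missing is an explicit early threshold for raising basal. Mealtime restart and rescue do not restore basal, and general discretion is not a rule for who should be spared the first cut.

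A reader might also take the text literally and confine the cut to PHN/TPM. The placebo point would then fall away, but the insulin change would reveal assignment to a blinded team, so the wording would still need correcting.

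**Conclusion.** The concern holds as a safety gap in a defined subset. Every prior insulin user has insulin reduced at week 0 without a glucose or A1c check. On the both-arms reading this includes placebo participants, and it includes those above the protocol's own 8.5% insulin-start level. The only basal increase with a stated threshold waits about 6 weeks at full tolerance. The documents do not give the number of insulin users among the 30 participants or their doses, so the overall size cannot be stated; the 20–60% day-one fall rests on assumed basal shares.

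A reader might infer that the Aim 2 A1c comparison is biased. It is not shown to be: the same rule in both arms keeps the randomised contrast valid, and any figure for an A1c shift would need a subset size and a loss of control that the documents do not supply. No effect on the primary BMI analysis follows either. Calling the comparator standard treatment fits less well for insulin-treated placebo participants, but that is a matter of description and does not carry the point. The change should be made because the participants are adolescents and the remedy is cheap.

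**What to change.** Amend the Insulin Therapy text in 4.1, with the same wording for both arms:

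1. State that in weeks 0–24 *PHN/TPM therapy* in the insulin rules means blinded study drug, PHN/TPM or placebo.
2. Do not apply the week-0 basal cut or the mealtime stop when baseline A1c is above 8.5%. These participants keep their dose and enter the existing 4-weekly reduction rule (FPG below 110).
3. At any CGM review from week 4, allow return to the entry basal dose if average FPG is above 185 mg/dL, without waiting for titration to end.

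Every trigger is an A1c or CGM value, so no step needs the randomization key, and both measurements are already scheduled. The main cost is timing: the baseline A1c result must be known before insulin instructions are given. Instructions could follow by telephone, or A1c could be added to the screening blood draw. The clinical cost is that PHN/TPM participants above 8.5% keep full insulin until the first CGM review; the down-titration for hypoglycaemia in 12.1 covers this.

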Insulin titration per CGM			X	X	X	X	X	X	X	X	X	X	X	X	X
Dispense new CGM sensor			X	X	X	X	X	X	X	X	X	X	X	X	
Dispense study medication		X	X	X	X	X	X	X	X	X	X	X	X	X	
Review of medication adherence					X			X			X				X
Review of co-administered drugs	X	X			X			X			X				X
Lifestyle and behavior counseling		X			X			X			X				X

Highlighted "X" will be done in the Clinical Research Unit. Non-highlighted X will be done in the Delaware Clinical Research Center

a Including height and weight at Weeks 0, 12, 24, 36 and 52. Weight only will be done at Weeks 4, 8, 16, 20, 28, 32, 40, 44, 48. Weight done remotely via Bluetooth monthly if there are no in-person visit scheduled for weeks 28, 32, 40, 44, and 48.

b Blood will be drawn during the OGTT at baseline, 30-, 60-, 90- and 120-minutes following glucose ingestion

c Continuous glucose monitoring with CGM data will be reviewed with participant via telephone after upload by PI or [name], Clinical Diabetes Educator.

d Urine pregnancy tests will be done on all females of childbearing potential. Tests will be done at in-person or at home.

\$ Visit windows for Weeks 4-52 are +/-7 days from the baseline visit

% In-person visits

5.2 Study Procedures:

Physical exam: A study physician will conduct a physical examination to ensure the participant is healthy enough to enroll in the study. A pubertal status will also be undertaken by the study physician ([name]) who is a trained pediatric endocrinologist. She has been trained in the proper technique to assess pubertal stages and will be the same study physician conducting all assessments throughout the trial.

Vital signs: Blood pressure (BP) and heart rate (HR) will be collected.

Hemoglobin A1c: Blood will be collected for a hemoglobin A1c level.

EKG: Electrocardiogram will be performed at screening/baseline visit and per PI discretion.

Eating Disorder Examination Questionnaire (EDE-Q): The EDE-Q identifies disordered eating behaviors and unhealthy attitudes about weight, such as purging, unhealthy obsession with dieting and/or body weight, prolonged fasting/starvation, use of laxatives to control weight and excessive exercise.

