Patient Health Questionnaire-9 (PHQ-9): The PHQ-9 measures depression and suicidality. The PHQ-9 Modified for Teens will be administered to participants < 18 years of age. A participant will be referred to a mental health professional or primary care provider if s/he has a PHQ-9 score of  $\geq 10$  or reports any suicidal behavior. A PHQ-9 score  $\geq 15$  at the screening vision is an exclusion criteria.

Columbia-Suicide Severity Rating Scale (C-SSRS): The C-SSRS measures depression and suicidality. A participant will be referred to a mental health professional or primary care provider if s/he has any suicidal behavior or any suicidal ideation of type 4 or 5 on the C-SSRS. Please see Exclusion Criteria for cut-off scores related to the C-SSRS.

Pediatric Quality of Life Inventory (PedsQL™): The PedsQL measures general and disease-specific quality of life. We will be using the participant-reported measures for the PedsQL™ Generic Core Scales and Diabetes Module Version 3.2 for young adults (aged 18-25 years) and Teens (12-18 years).

Oral Glucose Tolerance Test (OGTT): Insulin sensitivity and  $\beta$ -cell function will be measured via a 2-hour, 75 mg oral glucose tolerance test. OGTT has been widely used in the evaluation of  $\beta$ -cell dysfunction and T2D, including in the TODAY and RISE studies. The OGTT will be performed following a 10-12 hour overnight fast. Participants will take their last dose of metformin (if applicable) the evening before testing. Participants on basal or bolus insulin will be asked to withhold insulin dose either 36 hours or 6 hours, respectively, prior to testing. Plasma glucose levels, C-peptide, and insulin levels will be measured at baseline, 30, 60, 90 and 120 minutes following standard glucose ingestion. If a participant comes to a visit and has not withheld insulin for the required number of hours, the visit

will proceed without the OGTT and the participant will be asked to return to perform the OGTT within one week of the originally scheduled visit.

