Glycemic Control: Time in range (BG of 70-180 mg/dL) and hypoglycemic events will be measured using Continuous Glucose Monitors, either Freestyle Libre 14 day or Dexcom G7. The Freestyle Libre 14 day is no longer being produced so we will phase in the use of Dexcom G7 CGM. Worn on the skin, the disposable, single use sensor will continually measure glucose levels from the interstitium, every minute for 14 days (Libre) or 10 days (Dexcom G7) and will upload the data for review, and the participant will be asked to share this data with the study team. Participants will be taught how to place and replace the CGM. Participants who have a Libre CGM will be instructed to swipe the sensor at least twice daily (fasting and at bedtime) and to upload their CGM data monthly. Participants who have the Dexcom CGM will not need to swipe, but will be instructed to upload their CGM data monthly. CGM data will also be used to titrate insulin and metformin dosing. Percent time of CGM use will be used to assess adherence.

Total daily insulin dose: For participants on insulin therapy, total daily insulin dose (units/kg/day) will be averaged over the previous month at each study visits. Participants will log their insulin doses and return pens to study visits.

Body composition: Total body and visceral fat (% and kg) and measures of bone mineral density will be measured by dual energy x-ray absorptiometry (iDXA). iDXA measurements, using standard positioning techniques, will be conducted and analyzed by trained staff.

Anthropometrics: Height and weight will be collected by trained research staff at weeks 0, 12, 24, 36 and 52. Weight only will be collected at Weeks 4, 8, 16, 20, 28, 32, 40, 44, and 48. Weight will be collected via a scale provided to the participants and reported directly to the research coordinator at Week 28, 32, 40, 44, and 48 if there no monthly visits and per the PI's discretion.

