### 14.3 Statistical Analysis:

Descriptive analyses of baseline characteristics and outcomes will include means and standard deviations, median and range for continuous variables and frequencies for categorical variables. Treatment adherence will also be evaluated by the methods described above. Safety analyses will be primarily descriptive reporting the number and percentage of adverse events. All safety outcomes will be evaluated and monitored throughout the trial. Confidence intervals (CIs) and p-values will be based on robust variance estimation. Statistical significance will be considered as  $p < 0.05$ .

Aim 1: The primary analysis will be conducted using the ITT population to compare the mean BMI percent change (primary outcome measure) from randomization to 6 months of follow-up between the groups, adjusted for BMI at randomization for added precision. We hypothesize that with participants treated with PHN/TPM will demonstrate greater BMI percent change compared to controls at 6 months. Supportive analyses using the PP population will also be conducted along with consideration of adjustment for residual imbalances

between treatment groups after randomization (e.g., in sex as a biological variable). Longitudinal analyses will also be conducted, incorporating the multiple time points through the open-label extension (6 months to 12 months follow-up) during which these BMI measurements will be obtained. This will examine durability of changes observed over the masked portion of follow-up, as well as provide additional safety information. Supportive analyses using the PP population will also be conducted.

Aim 2: Secondary outcomes will be analyzed in the same fashion as the primary endpoint wherein analyses will be adjusted for values at randomization. Outcome measures for Aim 2 are c-peptide index ( $\Delta C_{30}/\Delta G_{30}$ ), insulin sensitivity (1/fasting insulin),  $\beta$ -cell function relative to insulin sensitivity (oral disposition index [oDI]), A1c (%), and total daily insulin dose (units/kg/day). We hypothesize that participants treated with PHN/TPM will demonstrate improved insulin sensitivity and  $\beta$ -cell function compared to those assigned to placebo as measured by OGTT, A1c and total daily insulin doses. Complementary secondary analyses will also be conducted for each secondary outcome as described for the primary outcome.

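### Total daily insulin dose is defined only for participants on insulin, and A1c and dose are tested apart although the section 4.1 titration shifts benefit from one to the other

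*Combined protocol and SAP*

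**What the plan says.** **Titration (section 4.1).**
- PHN/TPM paragraph: if average fasting glucose by CGM is above 185 mg/dL at full or maximum tolerated dose, "metformin therapy or basal insulin therapy will be started or titrated for a goal average FPG <110 mg/dL".
- Metformin paragraph: "a dose of 2000 mg daily will be targeted if CGM is > 185 mg/dL".
- Insulin paragraph, upward: "basal insulin therapy will be started or titrated up by 20% until for a goal average FPG <110 mg/dL".
- Insulin paragraph, downward: a 20% cut when study drug starts, "then by 20% every 4 weeks if average FPG is <110 mg/dL", and basal insulin stopped once it is below 0.2 units/kg/day. Mealtime insulin stops at the start and returns only for high post-meal glucose.

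**Timing.** The schedule of events has a row "Insulin titration per CGM" marked at every 4-weekly visit. Section 8.3 provides for contact about insulin or metformin changes at the 4-weekly visits between the main ones.

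**Outcome definition (section 5.2).** "For participants on insulin therapy, total daily insulin dose (units/kg/day) will be averaged over the previous month at each study visits". Nothing says what value a participant who is not on insulin receives.

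**Analysis (section 14.3, Aim 2).** A1c and total daily insulin dose are both named as measures of one hypothesis. On method: "Secondary outcomes will be analyzed in the same fashion as the primary endpoint wherein analyses will be adjusted for values at randomization". There is no joint analysis of the two and no table of escalations. Section 14.4 uses last observation carried forward for the primary analysis and treats secondary endpoints in like manner.

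**The concern.** A treat-to-goal rule is a reasonable clinical choice, but it links the two outcomes. If PHN/TPM lowers glucose, placebo participants cross 185 mg/dL more often and receive more metformin or insulin, which pulls their A1c down. Participants on PHN/TPM more often fall below 110 and have insulin cut, which lets their A1c drift up. The benefit is then shared between A1c and dose, and with 15 per arm each share is hard to detect alone.

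The dose definition adds a separate problem that needs no modeling. Whether a participant is on insulin at week 24 is a result of treatment. If only users are analyzed, the best responders drop out of the comparison and participants newly started on insulin enter it, so the arms compared are no longer the randomized ones. A participant not on insulin at randomization also has no defined baseline dose to adjust for.

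**Working it through.** **1. The plan's own power figure.** Section 14.2 gives SD 8.9, correlation 0.75, 15 per arm and 80% power for a 6% BMI difference. Residual SD = 8.9 × √(1 − 0.75²) = 5.887. Standard error = 5.887 × √(2/15) = 2.150. Power = Φ(6/2.150 − 1.96) = Φ(0.83) = 0.797. With 13.5 per arm and 6.3%, it is 0.794. The stated figures reproduce. They concern BMI only; none is given for A1c or dose.

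**2. What the dose definition does.** Take a participant on basal insulin only, at an assumed 0.5 units/kg/day, whose fasting glucose is below 110 at each review.
- Week 0: 0.5 × 0.8 = 0.40
- Week 4: 0.32
- Week 8: 0.256
- Week 12: 0.205
- Week 16: 0.164, below 0.2, so insulin stops

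The week-24 dose, averaged over the previous month, is 0. Read literally, section 5.2 gives this participant no value. If the blank were treated as missing under section 14.4, the week-12 value of 0.256 would be carried forward. Either way, coming off insulin is not counted as such.

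**3. Effect of a split, by hand.** Assume a benefit that would give 80% power on A1c if insulin were fixed: (1.96 + 0.8416) × √(2/15) = 1.023 residual SDs. Let a share f move to dose, in the same SD units. Then A1c power = Φ(1.023(1 − f)√7.5 − 1.96), and dose power uses f in place of 1 − f. For an equal-weight sum with within-arm correlation r, the effect is 1.023/√(2 + 2r).

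| f | A1c | dose |
|---|---|---|
| 0 | 0.80 | – |
| 0.25 | 0.56 | 0.10 |
| 0.50 | 0.29 | 0.29 |
| 0.75 | 0.10 | 0.56 |

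The sum has power 0.66, 0.51 and 0.41 at r = −0.3, 0 and +0.3, whatever f is. It beats A1c alone only if f > 1 − 1/√(2 + 2r), that is 0.15, 0.29 and 0.38. It beats dose alone only if f < 1/√(2 + 2r), that is 0.85, 0.71 and 0.62.

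**4. Simulating the rule.** All of these inputs are assumptions: benefit 30 mg/dL reached by week 8; half on basal insulin (median 0.5 units/kg/day); one metformin step worth 20 mg/dL, then 20% insulin increases every 4 weeks to goal; the same rule in both arms; mean fasting glucose over weeks 12 to 24 as the stand-in for A1c. There were 72 scenarios (start of escalation, insulin response, glucose mean and SD, review error), each with 4,000 trials of 15 + 15.
- Escalated: placebo 59%, PHN/TPM 36%.
- Contrast on the stand-in: median 14.8 mg/dL (4.6 to 19.4), against about 27 if nothing is raised; reversed in 0 of 72.
- Median power: A1c 0.28 (0.07 to 0.60), dose 0.28 (0.21 to 0.46), rank sum 0.59 (0.37 to 0.81).
- Dose power if only week-24 insulin users count: 0.21, lower in 72 of 72.

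Two separately coded models gave A1c 0.27, dose 0.28, joint 0.57 (dose 0.20 in users only), and A1c 0.37 to 0.39, dose 0.24 to 0.26, joint 0.57 to 0.58. If insulin is raised only while glucose exceeds 185, A1c is 0.42, dose 0.23 to 0.24 and joint 0.56 to 0.59.

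**5. Where the joint test does not help.** If nothing is ever raised, A1c alone is better (0.58 against 0.49). With weekly increases, dose alone is better (0.30 against 0.24). With a benefit of 15 mg/dL all three are weak: 0.11, 0.10 and 0.21 for A1c, dose and joint. A simpler model, raising insulin once per 4 weeks only above 185, moved less of the glucose contrast: 28.6 to 23.1, 28.2 to 21.7 and 28.6 to 19.8 mg/dL with 30%, 60% and 100% on insulin, that is 19%, 23% and 31%. The model above moved (27 − 14.8)/27 = 45%. As a rough guide, these shares lie on both sides of the 0.29 break-even at r = 0.

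**The case against.** The strongest reply is that the remedy rests on invented inputs. That is true of every power figure for A1c and dose. Adding mealtime insulin, which is part of total daily dose, shows how much they matter: one model then put the joint test ahead of A1c in only 54 of 72 scenarios (29 of 72 when insulin is raised only above 185), while another kept it ahead in 17 or 18 of 18. The size of the gain is therefore not settled.

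Second, A1c is already measured at week 12. Full dose is reached at about week 6 (three 14-day steps), so week-12 A1c largely precedes escalation. In one model a week-12 stand-in had median power 0.60 against 0.58 for the joint test, and 0.58 against 0.43 with mealtime insulin. This stands, though section 14.3 does not name week 12 for the secondary outcomes.

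Third, analyzing secondary outcomes as the primary implies ITT, which keeps escalated participants in. That fixes who is analyzed but not which value a non-user receives.

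Fourth, a rank sum has no clinical unit, ignores metformin and is one more unadjusted test. All of this is correct, so it can only be supplementary. The OGTT measures are partly protected, since "Participants on basal or bolus insulin will be asked to withhold insulin dose either 36 hours or 6 hours, respectively, prior to testing", but they do not settle a disagreement between A1c and dose.

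A reader might infer three stronger things that the documents do not support.
- That the titration rule is defective because section 4.1 gives an interval for cuts but none for increases. The schedule and section 8.3 imply 4-weekly increases, and barring changes between 110 and 185 mg/dL would be a clinical change.
- That the A1c result would be reversed. Under 4-weekly increases the simulations show dilution only.
- That the BMI result is affected. Nothing here bears on it.

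**Conclusion.** The point holds for a secondary aim. The firm part comes from the text alone: as written, the dose outcome leaves out participants who come off insulin, which conflicts with an ITT comparison, and separate tests of A1c and dose do not account for the titration that links them. The softer part is the gain from a joint analysis. It is roughly a doubling of median power under treat-to-goal with 4-weekly increases in two of the three models, and smaller in the third. It depends on assumed values for the benefit, the share on insulin, the insulin response and the correlation, and it shrinks or disappears if little benefit moves to dose or if A1c and dose are positively correlated. It supports adding an analysis, not replacing one.

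**What to change.** In sections 5.2 and 14.3:
1. Analyze week-24 total daily insulin dose in all ITT participants, counting 0 units/kg/day for anyone not on insulin, at randomization as well as at week 24. State that being off insulin is a value of 0 and not a missing value.
2. Report for each arm how many participants had metformin or insulin started or raised, which means logging the date and reason of each change.
3. Keep the planned A1c and dose analyses with their confidence intervals. Add one analysis labeled supplementary: rank participants on baseline-adjusted week-24 A1c and on baseline-adjusted week-24 dose, add the ranks, and compare arms with one two-sided 5% test (O'Brien rank-sum). Read it beside the week-12 A1c comparison.

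The cost is a short paragraph, a little more analysis and one more unadjusted supplementary test, whose result has no clinical unit and does not capture metformin changes. Visits, tests, the glucose goal and the section 4.1 rule stay as they are.
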